7.3 Treatment and Management of RMS

Patients with RMS are recommended to receive treatment with disease-modifying drugs (DMDs) to decrease the rate of relapse and slow the accumulation of brain lesions on MRI. Numerous immunomodulatory agents with differing routes of administration (including injectable, oral, and infusion) and mechanisms of action have been shown to have beneficial

effects. The medications that have received labels from the US Food and Drug Administration (US FDA) for the treatment of RMS include the intravenous medications natalizumab, ocrelizumab, alemtuzumab, and mitoxantrone; the injected medications interferon beta, glatiramer, ofatumumab, and daclizumab; and the oral medications diroximel fumarate, siponimod, ozanimod, monomethyl fumarate, dimethyl fumarate, teriflunomide, fingolimod, ponesimod, and cladribine tablets. Patients with relapsing-remitting multiple sclerosis (RRMS) typically require more than one DMD during their clinical course. Because they are not curative, most DMDs are generally continued indefinitely unless they are ineffective or not tolerated. There is currently no standard protocol to guide the choice of DMD for patients with MS. Rather, treatment decisions and medication choices are the result of a thorough risk-benefit analysis and consideration of disease activity, patient-specific factors, and drug-related factors (Pardo 2017).

CCI

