8.1 Primary Objective

To estimate the annualized relapse rate (ARR) over a 24-month period in patients with RMS, including RRMS and aSPMS, who are treated with cladribine tablets in a real-world setting and after suboptimal response to any other oral or infusion DMDs approved in the US for RMS.

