9.2 Setting

9.2.1 Study Population

The study population will be identified according to the below inclusion and exclusion criteria.

For inclusion in the study, all of the following inclusion criteria must be fulfilled:

1. Male or female patients ≥ 18 years
2. Signed informed consent
3. Have diagnosis of RMS, including RRMS and aSPMS, and satisfy the approved indication for cladribine tablets as per USPI
4. Have time since diagnosis of RMS of at least 12 months
5. In the opinion of the investigator, experienced suboptimal response (lack of effectiveness, intolerance, poor adherence) to oral DMD treatment other than cladribine tablets or infusion DMD treatment
6. Had received their last previous oral DMD for at least 1 month or at least 1 dose of their last previous infusion DMD
7. Have decided to initiate treatment with cladribine tablets during routine clinical care (i.e. before enrollment)
8. Meet criteria as per the approved USPI
9. Have access to a valid e-mail address

Patients are not eligible for this study if they fulfill any of the following exclusion criteria:

1. Have been previously treated with cladribine in any dosing form (intravenous, subcutaneous, or oral)

2. Transitioning from previous oral or infusion DMD solely for administrative reasons such as relocation
3. Have any clinical condition or medical history noted as contraindication on USPI
4. Are currently participating in an interventional clinical trial
5. Pregnant or breastfeeding women, women who plan to become pregnant or men whose partner plans to become pregnant during the cladribine treatment period

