9.3 Variables

The following variables will be collected:

Screening and/or Baseline Visit

- Patient demographics, including: age, sex, weight, self-reported race/ethnicity
- Date of diagnosis of MS, date of first symptoms of MS
- DMD treatments received prior to study enrollment, since MS diagnosis (including medication doses and routes of administration, start dates, stop dates, and reasons for discontinuation)
- Relapse of MS in the 2 years prior to the study period or since MS diagnosis, if diagnosis <24 months (including dates of onset and resolution of relapse)
- Most recent MRI results prior to starting cladribine tablets (baseline MRI), which is expected to have been taken within the prior 90 days
[REDACTED]
[REDACTED]
[REDACTED]
- Results of MRI in the 2 years prior to study enrollment or since MS diagnosis, if diagnosis <24 months
[REDACTED]
[REDACTED]
- Results of neurological examination as per standard of care (e.g., Kurtzke Functional System Scores (FSS), ambulation up to 500 meters and Expanded Disability Status Score [EDSS])
- Results of physical examination as per standard of care
- Hematology assessment (white blood cell count, hemoglobin, hematocrit, platelet count, ALC). If the investigator assesses
[REDACTED] or immunoglobulin levels, these data should be recorded as well
- Pregnancy, human immunodeficiency virus (HIV), hepatitis B, hepatitis C and tuberculosis test results
- ePRO assessments (treatment adherence questions based on modified versions of the MS-TAQ, TSQM, SF-36, MFIS-5, BDI-FS, WPAI-MS, PDDS)
- Comorbid conditions
- List of all MS symptomatic specific medications taken in the 2 years prior to study enrollment (or since MS diagnosis, if diagnosis <24 months), including medication start and stop dates and reasons for discontinuation

Follow-Up Visits

The anticipated timing of assessments is presented in Table 1: Schedule of Assessments.

- Medication log of cladribine tablets treatment during the study period, including medication start dates, medication stop dates, medication dose (mg), number of dose and reasons for discontinuation
- Medication log containing other MS DMD treatments (if applicable) during the study period, including medication doses and routes of administration, start dates, stop dates and reasons for discontinuation

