SF36v2_MH3	How much of the time during the past 4 weeks have you felt calm and peaceful?	All of the time	Most of the time	Some of the time	A little of the time	None of the time	
SF36v2_VT2	How much of the time during the past 4 weeks did you have a lot of energy?	All of the time	Most of the time	Some of the time	A little of the time	None of the time	
SF36v2_MH4	How much of the time during the past 4 weeks have you felt downhearted and depressed?	All of the time	Most of the time	Some of the time	A little of the time	None of the time	
SF36v2_VT3	How much of the time during the past 4 weeks did you feel worn out?	All of the time	Most of the time	Some of the time	A little of the time	None of the time	
SF36v2_MH5	How much of the time during the past 4 weeks have you been happy?	All of the time	Most of the time	Some of the time	A little of the time	None of the time	
SF36v2_VT4	How much of the time during the past 4 weeks did you feel tired?	All of the time	Most of the time	Some of the time	A little of the time	None of the time	
SF36v2_SF2	During the past 4 weeks , how much of the time has your physical health or emotional problems interfered with your social activities (like visiting with friends, relatives, etc.)?	All of the time	Most of the time	Some of the time	A little of the time	None of the time	
	How TRUE or FALSE is each of the following statements for you?						
SF36v2_GH2	I seem to get sick a little easier than other people.	Definitely true	Mostly true	Don't know	Mostly false	Definitely false	
SF36v2_GH3	I am as healthy as anybody I know.	Definitely true	Mostly true	Don't know	Mostly false	Definitely false	
SF36v2_GH4	I expect my health to get worse.	Definitely true	Mostly true	Don't know	Mostly false	Definitely false	
SF36v2_GH5	My health is excellent.	Definitely true	Mostly true	Don't know	Mostly false	Definitely false	
	SF-36v2® Health Survey © 1992, 2000, 2009 Medical Outcomes Trust and QualityMetric Incorporated. All rights reserved. SF-36® is a registered trademark of Medical Outcomes Trust. (SF-36v2® Health Survey Standard, United States (English))						

**MS-TAQ Modified version for once or twice daily oral dosing to assess adherence  
during last previous oral DMD treatment**

1.) Before enrolling in this study, what oral medication were you taking to treat your Multiple Sclerosis (MS)? (Check one)

Aubagio (teriflunomide)	
Gilenya (fingolimod)	
Tecfidera (dimethyl fumarate)	

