2.) During the last 4 weeks (28 days) that you were taking this medication, how many days were you supposed to take this medication? (Check one)

Twice a day (58 times)	
Once a day (28 times)	
Other, please specify:	

3.) Did you miss or forget to take any doses of this medication during the last 4 weeks (28 days) that you were taking the medication? (Check one)

Yes	
No	

4.) How many doses did you miss or forget to take? (Complete blank)

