**MS-TAQ Modified version to assess adherence during last previous infused DMD treatment**

1.) Before enrolling in this study, what infused/intravenous (IV) medication you were taking to treat Multiple Sclerosis (MS)? (Check one)

Tysabri (natalizumab)	
Ocrevus (ocrelizumab)	
Lemtrada (alemtuzumab)	

2.) During the time that you were taking this medication, how often in the past year (or the time that you were taking this medication if less than one year) were you supposed to take this medication? (Check one). If none of the choices below describe your exact dosing, please describe under Other.

Tysabri - Every 4 weeks	
Ocrevus - 1st month doses only	
Ocrevus - 1st month and 6-month doses	
Lemtrada - 5 days per year (1st year)	
Lemtrada - 3 days per year (subsequent years)	
Other, please specify:	

3.) Did you miss or forget to take any doses of this medication during the past year (or the time that you were taking this medication if less than one year)? (Check one)

Yes	
No	

4.) How many doses did you miss or forget to take? (Complete blank)

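### Question 1 of the baseline MS-TAQ has no valid answer for 6 of the 12 eligible DMDs that the protocol names, yet the SAP summarises it

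*SAP*

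**What the plan says.** **Who is eligible.** The primary objective (Protocol 8.1) covers patients treated "after suboptimal response to any other oral or infusion DMDs approved in the US for RMS". Inclusion criterion 5 (Protocol 9.2.1) requires a suboptimal response "to oral DMD treatment other than cladribine tablets or infusion DMD treatment". Neither restricts the previous drug to a shorter list. Protocol 7.3 names "the oral medications diroximel fumarate, siponimod, ozanimod, monomethyl fumarate, dimethyl fumarate, teriflunomide, fingolimod, ponesimod, and cladribine tablets" and "the intravenous medications natalizumab, ocrelizumab, alemtuzumab, and mitoxantrone" as labelled for RMS.

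**What the questionnaire offers.** SAP Section 18 reproduces the modified MS-TAQ versions. Question 1 of the oral version asks "Before enrolling in this study, what oral medication were you taking to treat your Multiple Sclerosis (MS)? (Check one"), with three drugs to choose from. Question 1 of the infused version asks "what infused/intravenous (IV) medication you were taking to treat Multiple Sclerosis (MS)? (Check one"), also with three. Question 2 of both versions, on dosing frequency, has a row "Other, please specify". So does question 1 of the cladribine version. Question 1 of the two baseline versions has none.

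**What is analysed.** SAP 16.4 summarises each MS-TAQ question descriptively, in all three versions and without imputation. SAP 11.3 also summarises the baseline MS-TAQ data as past treatment adherence. No text exempts question 1.

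**What else is recorded.** Protocol 9.3 has sites collect "DMD treatments received prior to study enrollment, since MS diagnosis (including medication doses and routes of administration, start dates, stop dates") together with reasons for stopping. SAP 11.3 tabulates each DMD received in the last two years from these data.

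**The concern.** A patient whose last oral or infused drug is not on the list can only leave question 1 blank or tick a drug that was not taken. A blank is visible, because SAP Section 9 shows missing values as their own category. A wrong tick is not: it enters the table as a valid answer. The planned summary then misstates which drug patients came from, and the SAP does not say which source prevails when question 1 and the site record disagree.

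The stake is one descriptive item within a secondary objective (adherence). The item matters mainly because it names the drug to which the other baseline adherence answers refer.

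**Working it through.** The plan gives no figure to reproduce on this point. The check is a count of drugs, followed by a look at what uses question 1.

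**Step 1: count the drugs.** Admitted drugs come from Protocol 7.3 and response options from SAP Section 18.

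| Route | Named in Protocol 7.3 | Admitted | Offered in question 1 | No option |
|---|---|---|---|---|
| Oral | 9 including cladribine | 9 − 1 = 8 | 3 | 8 − 3 = 5: diroximel fumarate, siponimod, ozanimod, monomethyl fumarate, ponesimod |
| Infused | 4 | 4 | 3 | 4 − 3 = 1: mitoxantrone |
| Total | 13 | 12 | 6 | 6 |

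As shares of drug names, this is 5/8 = 62.5% of oral, 1/4 = 25% of infused and 6/12 = 50% overall. These are not shares of patients.

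**Step 2: is a row lost in the PDF text?** Unlikely. The row for another answer is printed in question 2 of both baseline versions and in question 1 of the cladribine version. It is absent only where the previous drug is identified.

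**Step 3: how many patients?** The documents give no split by previous drug and no visible total sample size. The only group they size is the planned sub-cohort of about 100 direct switchers from ocrelizumab (Protocol 9.2.2), a listed option. An illustration therefore rests on assumptions:

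affected = (N − 100) × s, where s is the share of the remaining patients whose last drug is unlisted.

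| Assumed N | s = 0 | s = 10% | s = 30% | s = 50% |
|---|---|---|---|---|
| 150 | 0 | 50 × 0.1 = 5 (3.3%) | 15 (10.0%) | 25 (16.7%) |
| 200 | 0 | 100 × 0.1 = 10 (5.0%) | 30 (15.0%) | 50 (25.0%) |
| 300 | 0 | 200 × 0.1 = 20 (6.7%) | 60 (20.0%) | 100 (33.3%) |

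Percentages are of N. The range runs from 0 to 100 patients, so it bounds nothing useful. It shows only that the number depends on an unknown share.

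**Step 4: what depends on question 1?**

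- Previous-DMD table and reasons for discontinuation (SAP 11.3): built from the site-recorded DMD data.
- Ocrelizumab sub-cohort (Protocol 9.2.2, SAP 8.2): defined by the switch itself, and the drug is a listed option in any case.
- ARR: no link.
- MS-TAQ questions 2 to 7: answerable whatever is ticked in question 1.
- The question 1 summary under SAP 16.4: depends on it entirely.

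**The case against.** The strongest reply is that the study does not rely on this item. Sites record every DMD since diagnosis, the main data source is the medical record (Protocol 9.4), and SAP Section 9 already has a rule for partial dates of the last DMD. On this view question 1 is redundant, and the correct drug is already in the database. That stands, and it is why the severity is minor. It does not rescue the planned summary of question 1, which the SAP still calls for and which has no correct answer for six drugs.

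A reader might infer more than this, and four such inferences are not supported:

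- *The last previous DMD will be wrong or missing for many patients.* No split by drug is given, and the one sized group has an option. The defect lies in the questionnaire item, not in the study's record of previous treatment.
- *Missed doses will be credited to the wrong drug.* The visible SAP plans no adherence-by-drug table. This could arise only if someone later read adherence by the question 1 answer.
- *The question 1 table will contradict the previous-DMD table.* The latter counts every DMD in a two-year window and the former asks for one drug. They would differ even with a complete list of options.
- *Answers will be false rather than missing.* The documents do not show the live ePRO form or say whether question 1 can be skipped, so the mix of blanks and wrong ticks is unknown.

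**Conclusion.** The point holds in a narrow form. Question 1 of the baseline MS-TAQ cannot be answered correctly for 6 of the 12 admitted drugs that the protocol names, and the SAP plans to summarise it. For any patient last treated with one of the six, that entry will be wrong or missing. The number of patients cannot be derived from the documents and could be zero.

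This rests on two assumptions: that the versions in SAP Section 18 are those the patients saw, and that Protocol 7.3 reflects the admitted drugs. No primary, safety or treatment-pattern result is affected. Severity is minor.

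**What to change.** Amend SAP 11.3 and 16.4 in three respects:

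1. Exempt question 1 of the two baseline MS-TAQ versions from the single-question summaries.
2. Report the last previous oral or infusion DMD from the site-recorded eCRF data (name, start and stop dates) alongside the baseline adherence items.
3. List patients whose question 1 answer is blank or disagrees with the eCRF record.

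Adding a row for other drugs to the form would not help now: the last patient consented on 28 November 2022 (Protocol Section 6), so baseline answers have already been given. A breakdown of baseline adherence by drug is not needed to correct the plan. The cost is SAP wording and one merge of data already collected.

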**IF YOU HAVEN'T SKIPPED ANY DOSES IN THE PAST 28 DAYS, SKIP TO QUESTION 6**

**(Complete this section only if you missed a dose in the past 28 days)**

5.) How important were the following factors in missing or forgetting to take a dose? (Please check one answer for each)

	Not important at all	A little important	Moderately important	Extremely important
Memory problems	0	1	2	3
Too busy	0	1	2	3
Side effects of medication	0	1	2	3
Needing someone to help me take my medication	0	1	2	3
Ran out of medication or could not refill my prescription	0	1	2	3
Away from home and could	0	1	2	3

	Not important at all	A little important	Moderately important	Extremely important
not access my medication				
Feeling anxious, depressed, or nervous about taking my medication	0	1	2	3
Dissatisfaction with my medication	0	1	2	3
Did not want taking my medication to interfere with activities	0	1	2	3
Tired of taking my medication	0	1	2	3
Did not feel like taking my medication	0	1	2	3

6.) Overall, how hard or easy do you feel it is to take your most recent Multiple Sclerosis treatment as recommended by your physician? (Check one)

Extremely easy	1
A little hard	2
Moderately hard	3
Very hard	4
Extremely hard	5

7.) Overall, how satisfied are you with how things have been with your treatment during the past 4 weeks (28 days)? (Check one)

Not satisfied at all	1
A little satisfied	2
Moderately satisfied	3
Very satisfied	4
Completely satisfied	5

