9.7.3 Statistical Methods

Descriptive statistics will be used to summarize data. If the outcome in question is a continuous variable, the number of observations, number of missing values, mean, SD, median, first quartile and third quartile, minimum and maximum values will be presented; if the outcome is categorical, numbers and percentages of patients for each of the categories and numbers and percentages of missing values will be presented.

Where appropriate, 95% CIs will be presented. For continuous data, CIs for the mean will be calculated assuming a normal distribution of the data. CIs for binary endpoints will be presented using the Clopper-Pearson method.

Time to event data will be analyzed both descriptively as continuous data and through Kaplan-Meier analysis.

Primary Endpoint Analysis:

The ARR over the 24-month period will be presented, accompanied by the respective 95% CI.

Sensitivity analyses of the ARR will be performed considering the relapses as count data and using a negative binomial regression model with time as explanatory variables. A zero-inflated negative binomial regression model will be also considered.

Secondary Endpoints Analysis:

All secondary endpoints will be analyzed at Month 12 (interim analysis) and Month 24 (final analysis). Data will be summarized descriptively.

ARR (prospective assessment): The ARR over the 12-Month and 24-Month follow-up period after starting cladribine tablets will be presented, accompanied by the respective 95% CIs.

Other relapse analyses: The proportion of patients experiencing a relapse, ARR associated with hospitalization and associated with glucocorticoid use will be presented together with the corresponding 95% CI over the 24-month and over the 12-month period.

[figure not shown]
Treatment adherence: Treatment adherence, based on modified versions of the MS-TAQ, will be described at baseline (modified for once or twice daily oral dosing to assess adherence during last previous oral DMD treatment or modified for infusion dosing to assess adherence during last previous infusion DMD treatment), and for the first and second course of treatment with cladribine tablets during the first and second treatment year (modified for cladribine tablets).

Other PROs: For each ePRO score (TSQM-14, SF-36, MFIS-5, BDI-7, WPAI-MS, and PDDS), the actual value at each visit and change in scores from Baseline to Month 6, 12 and 24² will be described.

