### Treatment Adherence Questions

Seven treatment adherence questions, based on modified versions of the MS-TAQ, were developed to determine adherence and identify barriers to adherence for MS patients taking DMDs. A version of the MS-TAQ has been modified for once- or twice-daily oral dosing to assess adherence to the last previous oral DMD treatment at Baseline. Another version of the MS-TAQ has been modified to assess adherence to the last previous infused DMD treatment at Baseline. Finally, a version has been modified for cladribine tablets to assess adherence to cladribine tablets throughout the study.

For these versions, the single questions will be summarized descriptively. Items on an ordinal scale will be summarized as continuous variables. No imputation will be performed if any values in the MS-TAQ are missing.

The 3 modified versions of the MS-TAQ are reported in the Appendices.

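### SAP 16.4 summarises the ordinal MS-TAQ items Q5 to Q7 as continuous variables without category counts, so the tables will not show how many patients met each barrier or found treatment hard to take

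*SAP*

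**What the plan says.** SAP 16.4 analyses the modified MS-TAQ item by item: "the single questions will be summarized descriptively". It then adds "Items on an ordinal scale will be summarized as continuous variables". No total score is defined. The same section says the questions serve both to measure adherence and to find out what stands in its way.

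The forms in SAP Section 18 show the items concerned, in all three versions (previous oral drug, previous infusion, cladribine tablets):

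- **Q5**, "How important were the following factors in missing or forgetting to take a dose": four boxes scored 0 to 3 for each factor, with 11 factors in the oral and infusion versions and 10 in the cladribine version. It is restricted to patients who missed a dose; the oral and cladribine forms say "Complete this section only if you missed a dose in the past 28 days".
- **Q6**, in the oral version "Overall, how hard or easy do you feel it is to take your most recent Multiple Sclerosis treatment as recommended by your physician": five boxes scored 1 to 5, one labelled as easy and four as increasing grades of hard.
- **Q7**, in the oral version "Overall, how satisfied are you with how things have been with your treatment during the past 4 weeks (28 days": five boxes scored 1 to 5.

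SAP Section 9 lists the statistics for continuous variables: numbers of patients with and without a value, mean, SD, median, Q1 and Q3, minimum and maximum. Counts and percentages are kept for qualitative variables. Protocol 9.7.3 has a similar rule: "if the outcome is categorical, numbers and percentages of patients for each of the categories".

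**The concern.** Q5 is there to find out which obstacles matter. The natural result is a count: of the patients who missed a dose, how many said that side effects, memory or supply was an important reason? Likewise for Q6: how many found treatment hard to take? A mean of category codes does not answer either question, and with no total score there is no other summary of these answers. Response patterns with different practical meanings can share a mean, or can appear in an order that a reader would misinterpret. With 10 or 11 factors listed under one question, readers can be expected to compare them by mean or median.

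What is at stake is whether the secondary adherence endpoint can be used for its stated purpose.

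**Working it through.** The documents give no expected response distribution and no expected number of patients with a missed dose, so there is no figure of the plan to reproduce. The response patterns and the 40 patients below are assumptions. The codes (0 to 3, 1 to 5) are from SAP Section 18 and the list of statistics is from SAP Section 9.

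**Step 1: two barrier patterns for Q5.** Factor A: a share p tick 3 and the rest tick 0, so mean = 3p. Factor B: everyone ticks 1, so mean = 1. With p = 20% of 40 patients:

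| | Counts at 0/1/2/3 | Mean | SD | Median | Q1, Q3 | Min, max |
|---|---|---|---|---|---|---|
| A | 32/0/0/8 | 24/40 = 0.6 | 1.2 | 0 | 0, 0 | 0, 3 |
| B | 0/40/0/0 | 40/40 = 1.0 | 0 | 1 | 1, 1 | 1, 1 |

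A lies below B on the mean, the median and both quartiles, although 8 patients rated A extremely important and none rated B so.

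**Step 2: when this ordering holds.** On the mean, A lies below B only if 3p < 1, that is p < 1/3.

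| p | Mean of A | Median of A | Q3 of A | Mean relative to B |
|---|---|---|---|---|
| 10% | 0.30 | 0 | 0 | below |
| 20% | 0.60 | 0 | 0 | below |
| 30% | 0.90 | 0 | 3 | below |
| 33% | 0.99 | 0 | 3 | below |
| 34% | 1.02 | 0 | 3 | above |
| 40% | 1.20 | 0 | 3 | above |
| 49% | 1.47 | 0 | 3 | above |

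The median puts A below B for every p under 50%. Q3 shows the subgroup once p exceeds about 25%. SD and maximum differ between A and B at every p.

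**Step 3: can the counts be recovered from SD, quartiles and range?** Not in general. Four category shares that sum to 1 leave three unknowns, and mean and SD fix only two. Take two other assumed sets of answers from 40 patients:

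- 31/6/0/3: sum = 6 + 9 = 15; sum of squares = 6 + 27 = 33.
- 33/0/6/1: sum = 12 + 3 = 15; sum of squares = 24 + 9 = 33.

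Both give mean 15/40 = 0.375, SD = √[(33 − 15²/40)/39] = 0.84, Q1, median and Q3 all 0, minimum 0 and maximum 3. Every planned statistic agrees, yet 3 of 40 patients in the first set and 7 of 40 in the second chose one of the two upper categories.

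**Step 4: Q6.** 75% at 1 and 25% at 5 gives mean 0.75 + 1.25 = 2.0, the same as everyone answering 2 (a little hard). With 80% at 1 and 20% at 5, the mean is 0.8 + 1.0 = 1.8 and the median 1, lower than for that uniform answer (2.0 and 2). SD (1.6 against 0) and maximum (5 against 2) do differ. Q7 has the same format, so different distributions can share a mean there too.

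**Step 5: denominator for Q5.** SAP Section 9 bases proportions on the analysis population unless otherwise stated, with missing values in the denominator. For tables tied to a visit it uses the patients still in the study. Patients who correctly skip Q5 would then count as missing. If a share m of patients missed a dose, a barrier important to a share p of them would be printed as p × m. The denominator therefore has to be stated.

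**The case against.** Several counter-arguments have force.

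- **No ranking is planned.** Correct. A reader might infer that the plan will put the barriers in the wrong order, but neither document orders them. Misordering could arise only if a reader compares factors by mean or median.
- **The reversal is conditional and the example extreme.** Also correct. A reader might infer that a factor decisive for any minority always falls below one that is trivial for all. On the mean that fails from one third upward, and the response patterns are assumed.
- **SD and maximum reveal a split.** In part. They would alert a careful reader in Steps 1 and 4, but Step 3 shows that they need not give the number of patients in a category.
- **There is no clear breach of the protocol.** A reader might infer that SAP 16.4 contradicts protocol 9.7.3. The protocol does not say whether scored ordinal items count as categorical, and it leaves further detail to the SAP. The SAP also treats the MFIS-5 and BDI-FS items and the PDDS as continuous, so the convention looks deliberate. The tension with 9.7.3 is therefore soft.
- **The ordering argument concerns Q5 only.** Agreed. For Q6 and Q7 the point is that different distributions can share a mean. The lopsided labels of Q6 belong to the instrument and are not an error of the SAP.

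What remains is that no planned statistic reports how many patients chose each answer. For the MS-TAQ that is the information its purpose calls for. The SAP already provides this kind of table elsewhere: in 15.3, ALC is also shown as the proportion of patients in each lymphopenia grade.

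**Conclusion.** The point holds as a gap in reporting. SAP 16.4 and Section 9 together produce no category counts for Q5 to Q7, so the number of patients who rated a barrier as important, or who found treatment hard to take, cannot be read from the planned statistics. The means and medians are legitimate summaries of the codes; they are insufficient on their own.

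The importance is minor. It affects the presentation of a descriptive secondary endpoint. The missed-dose items (Q3 and Q4), the tablet-based compliance in SAP Section 13 and the primary ARR analysis are unaffected. The size of any misreading depends on response patterns and a number of Q5 respondents that the documents do not give.

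**What to change.** Add to SAP 16.4, after the sentence on ordinal items: *Q5, Q6 and Q7 will also be presented as number and percentage of patients in each response category; for Q5 the denominator is patients reporting a missed dose.*

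Mean and median may stay. No ranking rule and no cut-off for an important barrier are needed, and the documents would not support a particular one. The cost is one sentence and slightly longer tables. No new data are required.
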